10.2 Sample Size and Randomization

Sample size is not required and there will be no randomization.

10.3 Outcomes

One exploratory outcome is to determine if primary care providers take priorities from the priority setting note on the electronic medical record and make changes in care as a result of the priorities. This will be analyzed through chart reviews.

11 DATA COLLECTION AND QUALITY ASSURANCE

11.1 Data Collection Forms

The PPC facilitator will use the PPC manual to facilitate goal setting with all patients. Goals will be documented in the patient form that the patients take home and will be added to the electronic medical record under the PPC heading for primary care providers to review.

11.2 Data Management

Data related to priorities identification and care alignment will be pulled from the electronic health record to evaluate the feasibility of the intervention.

We will use Redcap to conduct the patient and clinician evaluation of the PPC approach. These responses will be securely stored in the UTMB research server.

11.3 Quality Assurance

10.3.1 Training

The PPC facilitator is certified in the PPC approach. [name] and [name] will use existing manuals to train clinicians on the PPC approach. Evaluations of fidelity will be conducted after 5 patients go through the PPC approach.

10.3.2 Metrics

We will conduct a chart review of all enrolled subjects and assess charts following care alignment steps for each of the following adverse events: urgent care visits, emergency department stays, and hospital admissions. If one of these events occurs, we will carefully review the charts to determine if any change in care results in clinical changes that contributed to the adverse event.

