7.1.4 Completion/Final Evaluation

The care alignment visit is considered the final visit.

8 **SAFETY ASSESSMENTS**

A participant is enrolled if he/she completes the care alignment visit. No adverse events are expected given that only goal setting and care alignment will be performed as part of routine clinical visits.

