8.1 Specification of Safety Parameters

We will monitor charts of enrolled subjects to track for any adverse events related to changes in care arising from care alignment procedures that differ from routine guidelines.

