8.3 Adverse Events and Serious Adverse Events

Adverse Event (AE): We will review charts from any potential AEs including urgent care visits, emergency department or hospital stays occurring after the care alignment step of PPC.

Serious Adverse Event (SAE): The intervention will not result in any of the following events, thus no SAE are expected. If a death occurs while the study participant is actively in the study this will be reported within 48 hours of occurrence or as soon as the study team finds out about the event.

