8.3.1 Follow-up for Adverse Events

[name] or [name] will record all reportable events with start dates occurring any time after informed consent is obtained until 7 (for non-serious AEs) or 30 days (for SAEs) after the last day of study participation. At each study visit, the investigators will inquire about the occurrence of AE/SAEs since the last visit. Events will be followed for outcome information until resolution or stabilization.

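### The protocol promises to track any adverse event from alignment-driven care changes, but after the alignment visit it specifies a search for only three acute-care encounter types

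*Combined protocol and SAP*

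**What the plan says.** The safety text sits in several places of the protocol; the SAP adds nothing on adverse-event ascertainment.

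- **8.1 (scope).** Charts of enrolled subjects are monitored to "track for any adverse events related to changes in care arising from care alignment procedures that differ from routine guidelines".
- **8.3 (definition).** "We will review charts from any potential AEs including urgent care visits, emergency department or hospital stays occurring after the care alignment step". The wording is open-ended, but the only examples are acute-care encounters.
- **10.3.2 Metrics (chart search, printed under 11.3).** Reviewers will "assess charts following care alignment steps for each of the following adverse events: urgent care visits, emergency department stays, and hospital admissions". Attribution follows from that list: "If one of these events occurs, we will carefully review the charts to determine if any change in care results in clinical changes".
- **8.3.1 (direct inquiry and window).** "At each study visit, the investigators will inquire about the occurrence of AE/SAEs since the last visit". Events are recorded from consent "until 7 (for non-serious AEs) or 30 days (for SAEs) after the last day of study participation".
- **7.1.4 (end of visits).** "The care alignment visit is considered the final visit".
- **Section 4 and 7.1.3 (contact after alignment).** One call to the patient, 2 weeks after the primary care visit, to assess satisfaction and evaluate the process. No adverse-event question is mentioned.
- **10.3.3 and 10.3.4 (quality assurance).** The fidelity review asks whether protocol deviations led to adverse events. A fuller chart review follows any adverse event, and events that arise from a care change go to the IRB.

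**The concern.** The intervention works by changing care. The SAP names medications, tests and referrals as the changes it will count, and protocol 3.1 describes an approach led by patient priorities rather than by single-disease guidelines. If such a change causes a problem, the problem need not end in urgent care, an emergency department or a hospital bed. It may be a symptom noted at a routine clinic visit, a fall managed at home and mentioned by phone, or a change that is undone because it did not go well. These fall within 8.1 but not within the list in 10.3.2.

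What is at stake is reporting. Under 10.3.4 the IRB hears of adverse events that arise from a change in care, so an event that nobody is instructed to look for may not reach it. Any later statement about the safety of the adapted approach would rest on the same search. In the feasibility phase the patients have dementia, which makes unprompted self-report a weak substitute for a specified search.

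**Working it through.** The plan states no event rate, sample-size calculation or safety estimate, so there is no figure to reproduce. The check sets the passages side by side and works out the recording window.

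**Step 1. Scope against search.** 8.1 covers any adverse event linked to certain care changes. 10.3.2 searches for three encounter types and makes attribution conditional on one of them. 8.3 does not repair this: it is open in principle but names no further event type and gives no search instruction. 8.2, whose heading promises methods and timing, describes what chart reviewers did in prior studies and sets out no search for this one.

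**Step 2. Does another route find a non-acute harm after alignment?**

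| Route | Limited by encounter type? | Finds a non-acute harm after alignment? |
|---|---|---|
| 10.3.2 chart search | Yes, three types | No |
| 8.3.1 inquiry at study visits | No | No: the last visit is the alignment visit |
| 2-week call (Section 4, 7.1.3) | Not applicable | Not as written: no adverse-event question is stated |
| 10.3.3 fidelity review | No | Only if it resulted from a protocol deviation |
| 10.3.4 monthly review | Not applicable | No: this part checks fidelity |
| 10.3.4 review after an adverse event | No | No: it starts from an event already known |

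The inquiry in 8.3.1 is the widest route, but it ends on the day the care changes are made.

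**Step 3. The recording window.** Take the alignment visit as day 0; the call is then on day 14. The last day of participation is not defined. 7.1.4 points to the alignment visit, while Section 7 counts the telephone follow-up as part of the intervention.

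- If the last day is the alignment visit: non-serious window closes on day 0 + 7 = 7; serious window on day 0 + 30 = 30. The non-serious window closes 14 − 7 = 7 days before the call.
- If the last day is the call: non-serious window closes on day 14 + 7 = 21; serious window on day 14 + 30 = 44.

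Under the first reading, a non-serious event that starts between day 7 and the call falls outside the recording window even if the patient mentions it. Under either reading, no study visit falls after day 0.

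**Step 4. Number of charts.** 10.3.2 already reviews every enrolled subject: 5 (adaptation) + 20 (feasibility) = 25.

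**The case against.** The best case for the plan is that 10.3.2 is a quality-assurance metric, a minimum list of readily countable events inside the wider scope of 8.1 and 8.3. On that view 8.3.1 supplies the general inquiry and 10.3.4 reviews any adverse event whatever its setting. This stands in part. It would be wrong to infer that the study looks for nothing beyond three encounter types, or that a fall treated at home could never be reviewed. Once such an event is known, 10.3.4 applies to it. What does not stand is that these routes would find it: 10.3.4 needs an event already known, and the 8.3.1 inquiry stops at alignment unless the call is treated as a study visit. The call is described under the follow-up visits heading, but 7.1.3 distinguishes it from the visit and 7.1.4 places the final visit before it.

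A reader might also infer that the count is inflated because 10.3.2 treats every hospital admission as an adverse event, planned ones included. That is largely answered by the text. Admissions are screened first and then reviewed for the contribution of a care change, and only events arising from such a change go to the IRB.

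Two further points have force. Safety is not a listed outcome and no harm rate is to be estimated, so the consequence is for monitoring and reporting, not for a planned analysis. And 8.4 refers to a separate data safety monitoring plan, which is not among the documents and may contain the missing detail.

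**Conclusion.** The mismatch is real and should be corrected. As written, 8.1 promises more than 10.3.2 searches for, and after the alignment visit non-acute harms have no specified ascertainment route. Followed literally, the plan would tend to under-detect them and so to under-report to the IRB.

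The size cannot be stated. A reader may be tempted to put a share on the harms that go unseen, but the documents give neither the number of harms expected nor the proportion that reach acute care, so any percentage would only restate an assumption. Nor do they support saying that all such harms will be missed: an event volunteered on the call or noticed incidentally in a chart could still be reviewed.

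The conclusion rests on three readings: that the list in 10.3.2 is applied as written, that the 2-week call is not a study visit in the sense of 8.3.1, and that the separate monitoring plan does not already fill the gap.

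**What to change.** Reconcile 8.1, 8.3, 8.3.1 and 10.3.2 so that scope, search and timing agree.

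1. Extend the chart review in 10.3.2. At any documented contact after alignment, flag adverse events plausibly linked to a change made at the alignment visit, including documented reversal of that change because of a problem. Any flag starts the attribution review. Tying the flag to an alignment-visit change matters: flagging every new symptom in patients with dementia and three or more chronic conditions would be broader than needed.
2. Add an adverse-event question to the 2-week call already planned.
3. Define the last day of participation so that the recording window in 8.3.1 covers that call.
4. Optionally, record each admission as planned or unplanned.

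If the separate monitoring plan already contains any of this, a cross-reference from 10.3.2 will do for that part.

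The cost is a few fields on about 25 charts already under review and one question on an existing call. Abstraction takes slightly longer, and the raw adverse-event count will rise and include some background illness, which the attribution review must sort without a comparison group.

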10.3.3 Protocol Deviations

Chart reviews of all enrolled subjects will focus on fidelity to the Patient Priorities Care processes. We will apply a PPC fidelity template to track any potential protocol deviations. We will also assess if these deviations resulted in any adverse events.

10.3.4 Monitoring

We will review charts on a monthly basis to ensure that the priorities identification process and the care alignment processes are occurring based on our established PPC fidelity rubric. We will also conduct a thorough chart review after any instance of an Adverse Event or SAE. The chart review will assess whether the AE/SAE occurred following any care alignment driven changes in treatment/care. AEs arising from a change in care will be reported to the IRB.

12 PARTICIPANT RIGHTS AND CONFIDENTIALITY

12.1 Institutional Review Board (IRB) Review

This protocol and the informed consent document (Appendix 1) and any subsequent modifications will be reviewed and approved by the IRB responsible for oversight of the study. For participants with dementia unable to consent verbal assent will be obtained and the caregiver will provide consent.

12.2 Informed Consent Forms

Consent forms will be Institutional Review Board (IRB)-approved in English and Spanish and the participant will be asked to select language of preference and read and review the document. Consenting will be done over the phone by the research coordinator before scheduling the goal setting meeting. The investigator will explain the research study to the participant for the adaptation phase (n=5) and to the person with dementia in the second phase (n=20) and answer any questions that may arise. A verbal explanation will be provided in terms suited to the participant's comprehension of the purposes, procedures, and potential risks of the study and of their rights as research participants. Participants will be informed that participation is voluntary and that they may withdraw

from the study at any time, without prejudice, and that the quality of their medical care will not be adversely affected if they decline to participate in this study. Participants will have the opportunity to carefully review the written consent form and ask questions prior to signing. The participants will be given a copy of the ICF so that they may discuss the study with their family or surrogates or think about it prior to agreeing to participate. The informed consent process will be conducted and documented in the source document (including the date), and the form signed, before the participant undergoes any study-specific procedures. A copy of the signed informed consent document will be given to the participants for their records. For participants with dementia, PCP will be asked about decision capacity. If they are deemed unable to consent, verbal assent will be obtained and consent will be provided by the caregiver. Copy of the signed ICF will be provided to the caregiver.

12.3 Participant Confidentiality

Data, forms, recordings, and other records that leave the site will be identified only by a participant identification number (Participant ID, PID) to maintain confidentiality. All records will be kept in a locked file cabinet. All computer entry and networking programs will be done using PIDs only. Information will not be released without written permission of the participant, except as necessary for monitoring by IRB, the FDA, the NIA, and the OHRP.

12.4 Study Discontinuation

The study may be discontinued at any time by the IRB, the NIA, the OHRP, the FDA, or other government agencies as part of their duties to ensure that research participants are protected.

13 ETHICAL CONSIDERATIONS

The ethical principles of the current study are based largely on the recommendations of the National Commission for the Protection of Human Subjects in Biomedical and Behavioral Research (the Belmont Commission), established by the 1974 National Research Act, American regulations governing the conduct of biomedical research involving human participants were published in 1981 by the federal Department of Health and Human Services (DHHS) (at that time, the Department of Health, Education and Welfare). Most US health care institutions have adopted the DHHS regulations, as subsequently amended, as a Common Rule to protect human participants in any research protocol that those agencies sponsor.

PUBLICATION OF RESEARCH FINDINGS

Publication of the results of this trial will be governed by the policies and procedures developed by the IMPACT Collaboratory. Any presentation, abstract, or manuscript will be made available for review by the sponsor prior to submission.

15 SUPPLEMENTS/APPENDICES

Statistical Analysis Plan

NCT05303194

Patient priorities care (PPC) will be initially incorporated in the workflow of a Geriatrics outpatient clinic at The University of Texas Medical Branch (UTMB). The PPC approach will be culturally adapted for older Hispanics in Texas by testing it in 5 Hispanics with multiple chronic conditions (MCC) and normal cognition. Five patients will receive the intervention and then the study team will make clarifying edits to materials and processes to finalize adaptations to the 6-step toolkit for conducting PPC with Hispanics. Once the PPC team and the advisory team have completed all changes, a feasibility study with 20 Hispanics with cognitive impairment in the same clinic at UTMB.

The primary objective of this pilot proposal is to adapt PPC for Hispanics. A secondary objective is to test the feasibility of using it on Hispanics with dementia. We will thus adapt and test PPC with 5 Hispanics and then test the adapted version with 20 Hispanics with dementia. One exploratory outcome is to determine if primary care providers take priorities from the priority setting notes on the electronic medical record and make changes in care as a result of the priorities. This will be analyzed through chart reviews.

This pilot project is not intended to identify specific outcomes resulting from the PPC approach; thus, no power calculations are needed. We will use descriptive statistics to examine frequency distributions and proportions for all quantitative variables. We will calculate effect sizes for changes in our exploratory outcomes (changes in medications, changes in tests and other referrals, changes specifically aligned to an identified patient priority). Interviews with practice-based implementation team members will be performed by [name] and analyzed using directed content analysis. Quantitative and qualitative findings will be triangulated using standard content analysis methods to create meta-themes that synthesize the quantitative and qualitative findings. The inclusion of 20 subjects is therefore sufficient to direct content analysis with the expectation that we will obtain data saturation of each content area.
